6. BENEFITS

Potential Benefits of the Proposed Research to the Subjects and Others: Participants may benefit from reduced weight gain and reduced physical, psychological and social morbidities and mortality associated with excess weight, the potential psychological and social benefits of participating in a treatment program, and the potential health benefits of improved diet and activity behaviors. Other children and the public may benefit from the potential scientific and public health impact of the knowledge that may result from this study. The potential benefits to the subject and to others outweigh the potential risks.

7. PRIVACY AND CONFIDENTIALITY

All participant information and specimens are handled in compliance with the Health Insurance Portability and Accountability Act (HIPAA) and privacy policies of Stanford University, Stanford Health Care, and Stanford Children's Health.

Wise Social Psychological Interventions to Improve Outcomes of Behavioral Weight
Control in Children With Obesity

Statistical Analysis Plan

NCT04422951

May 13, 2022

Study Design: two-arm, parallel group, randomized controlled trial.

Primary Hypothesis: Compared to children randomized to receive a usual care behavioral pediatric weight management program alone, children randomized to receive a usual care behavioral pediatric weight management program plus the wise social psychological interventions will have a significantly attenuated BMI trajectory over 6 months.

Primary Outcome: Body mass index (BMI) trajectory over the 6-months duration of the study for each participant.

Primary Analysis, Statistical Model and Approach: We will use mixed effects linear regression techniques to address our aims. Such models are typically utilized in the clinical trials setting where repeated measurements are proposed.^{154,155} Specifically, we will regress BMI at a given time point on study arm, days since randomization, and an interaction between study arm and days since randomization. Also included in the model are a subject-specific random effect to account for the correlation of measurements over time within a subject and a group-specific random effect to account for the correlation among outcomes across subjects assigned to the same group and behavior coaches. Both random effects are assumed to be normally distributed. Finally, we include the randomization factors: sex and race/ethnicity. The proposed model can be expressed as:

$$\text{BMI}_{ij} = \beta_0 + \gamma_i + \delta_{j(i)} + \beta_1 \text{ treatment}_i + \beta_2 \text{ time}_{ijk} + \beta_3 \text{ treatment}_i \times \text{time}_{ijk} + \beta_4 \text{ sex}_i + \beta_5 \text{ ethnicity}_i + \varepsilon_{ijk},$$

where ε_{ijk} is the random error term assumed to follow a normal distribution for the k^{th} observation corresponding to the i^{th} child assigned to the j^{th} group, γ_i is the subject-specific random intercept corresponding to the i^{th} child, and $\delta_{j(i)}$ is the group-specific random intercept corresponding to the j^{th} group in which the i^{th} child is nested. We are interested in drawing inference around β_3 that represents the difference in BMI trajectory over time between the two study arms. For this purpose, we will use a two-sided Wald test at the 0.05 level of significance. Our mixed effects regression approach most closely matches the study design and stratified randomization, and has advantages over a t-test endpoint analysis and other repeated measures analysis approaches for trial data including repeated measures ANOVA; it uses all available data, can accommodate differential lengths of follow-up, irregular measurement intervals, and missing data under reasonably flexible assumptions regarding the missing data mechanism.^{156,157}

Intent-to-Treat: We will adhere to intent-to-treat principles. All participants randomized will be included in the analysis and analyzed according to their original treatment assignment. While we expect limited loss to follow-up, our analysis allows subjects without complete data to be included in the analysis for their partially observed period. Such an analysis relies on a flexible assumption about missingness, namely that the data are missing related to observed features only (MAR). As a sensitivity analysis, we will also rely on multiple imputation-based methods that repeatedly impute values for those with incomplete data prior to fitting the mixed effects linear regression model. The imputation model can consider a large number of features (beyond those included in the primary analysis model). The sensitivity analysis will provide insight into the robustness of our findings to missingness and how missing data are handled.

Detectable Difference, Sample Size, and Power: We will randomize a total of 160 participants (80 per study arm). We estimate sufficient power to address our aims. Estimates of power were performed using simulations (1000 simulations per scenario), which allowed us to consider a wide range of plausible assumptions and conditions, varying the sample size, retention rates, ICCs within individuals, ICCs within groups, BMI standard deviations, and combinations of trajectories of BMI decreases and increases and in the treatment and control groups. Across a wide range of assumptions and our planned total sample size of 160 children, or 80 children per study arm, we have at least 80% power to detect clinically meaningful differences in trajectories of 0.4 kg/m² or greater per 24 weeks. For example, a 0.6 BMI increase over 24 weeks in the control group and a 0.2 BMI increase over 24 weeks in the treatment group.

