1. PURPOSE OF THE STUDY

a. Brief Summary

Weight loss interventions for children and their families often have variable outcomes and are hindered by low attendance or relapse. We will test if brief social psychological interventions (termed “wise” interventions) designed to overcome psychological barriers may improve participants' efforts toward a weight management program, their attitudes about themselves and their weight, and their weight control.

b. Objectives

We seek to improve outcomes of pediatric weight control interventions by adding novel, yet brief (less than 20 minutes) activities to pediatric weight management for children with obesity.

These wise interventions have proven very successful in improving school performance in children but are only recently have been applied to health behavior change. If found to be effective, these activities can easily be added to standard weight control interventions to increase their effectiveness and would be a major contribution to improving immediate and long-term health and well being of children seeking treatment for obesity.

c. Rationale for Research in Humans

The purpose of the study is to test the efficacy of new strategies for enhancing weight management in children with obesity and their families.

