After children and parents complete assent and consent forms, they will be asked to complete all survey measures including demographics, household composition, physical activity and eating habits, screen use, puberty stage, overconcern with weight or shape, school grades, and psychosocial measures. Children and parents will be encouraged to complete online REDCap surveys on separate devices. The research coordinator will review all surveys for completeness before ending the call. Parents will be asked to schedule a second zoom call within the upcoming 3 weeks. An electronic cellular-connected scale (BodyTrace), a tape measure to measure height, and a food portion size booklet to use during the dietary recall will be mailed to participants. Parents will be emailed a lab requisition for their child to have fasting blood tests collected at their local Quest labs.

Measures in baseline appointment – part 2

During the second Zoom video appointment, child's and parent's heights and weights will be measured using the mailed tape measure and electronic scale, and children will complete a 24-hour dietary recall. Child weight measurements will be used to determine child's eligibility into the study (≥ 95 th BMI percentile for age and sex). After finalizing eligibility and completing all baseline measures, participants will be randomized.

Randomization:

Families will be randomized to treatment conditions after completing baseline measures, using Efron's biased coin randomization stratified by location, sex, and race/ethnicity, to promote balance on key characteristics that may influence weight changes, and allow examination of sex as a biological variable. Investigators and all data collection staff will

remain blinded to treatment condition assignment until all participants have completed the final follow-up assessments.

Interventions:

The research activities will be delivered as online videos and activities sent 9 times throughout the program. Parents will be emailed REDCap surveys that link to Qualtrics activities; one with a parent video/activity and one with a child video/activity. The WISE interventions encourage values affirmations and a growth mindset. The control videos and activities reinforce diet and physical activity messages that are part of the weight control program.

Follow-up Assessments

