- We should avoid interim analyses and unnecessary "alpha-spending," which reduces the power of the study.
- Study participants in both treatment groups are being provided with beneficial interventions.

The Safety Officer may request an interim analysis at any time during the study for purposes of assessing safety/harm.

The study will be terminated if there is clear evidence of harm or harmful side-effects of the treatment or participation in the study that outweighs evidence of the benefits of participation. Each Safety Officer report (approximately every six months) will conclude with a recommendation to continue or to terminate the study. A copy of this letter will be forwarded to the IRB and the NIH Program Officer. A termination recommendation may be made by the Safety Officer at any time during the study if deemed necessary.

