In our previous research we have offered similar levels of compensation. Families have told us that financial compensation is not necessary or an important reason for joining the study but they do appreciate this expression that we value their time and participation in the measures. In our experience, these payments do not constitute undue pressure to participate in the study.

k. Costs to Participants

Participants are not charged for participation in the research study.

l. Planned Duration of the Study

Each child and parent/guardian will participate for a total of 6 months.

(i) Screening

Pre-screening online is estimated to take less than 15 minutes.

(ii) Active Participation in the Study

Baseline: Explanation of the study, confirmation of eligibility, completion of the consent/assent, and baseline measures will occur face-to-face via two Zoom calls. Estimated time = 90-120 minutes.

Intervention activities are sent to families by Qualtrics links via REDCap 9 times (throughout the 6 months study). Activities include short videos which range in length from 45 seconds to 5 minutes and/or a Qualtrics reading and writing activity that should take less than 15 minutes.

Follow-up Assessment Appointments: Face-to-face via Zoom follow-up assessments will occur approximately three months and six months after randomization. At the 3 and 6-month assessments, surveys will be administered, diet recalls collected, and height and weight will be measured. After six months, blood test requisitions will also be emailed. Estimated time for the 3- and 6-month Zoom appointments is 60 minutes.

(iii) Analysis of Participant Data

We anticipate keeping this protocol active for at least 10 years (5 years beyond the end of participant involvement) to complete data analysis and paper writing.

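### The SAP's primary hypothesis names usual care alone as the comparator, while the protocol gives the control arm study-delivered diet and activity content; the two should be reconciled and the hypothesis worded to match

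*SAP*

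**What the plan says.** **SAP, Primary Hypothesis.** The comparator is introduced as "Compared to children randomized to receive a usual care behavioral pediatric weight management program alone". The other arm receives a "usual care behavioral pediatric weight management program plus the wise social psychological interventions".

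**Protocol 2a, Interventions.** The research activities are online videos and tasks sent 9 times. The wise versions promote values affirmation and a growth mindset. For the other arm: "The control videos and activities reinforce diet and physical activity messages that are part of the weight control program".

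**Protocol 4l(ii), Active Participation.** A single schedule is given without separating the arms: "Intervention activities are sent to families by Qualtrics links via REDCap 9 times".

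**Protocol 2g, Study Endpoint(s).** Among the reasons for having no interim efficacy analysis: "Study participants in both treatment groups are being provided with beneficial interventions".

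**SAP, Primary Analysis.** Inference is on β₃, defined as "the difference in BMI trajectory over time between the two study arms" and tested two-sided at 0.05.

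The SAP does not mention control videos or activities anywhere.

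**The concern.** The two documents give different accounts of what control children receive. In the SAP it is the clinical program and nothing else. In the protocol it is that program, in which all children are already enrolled, plus study-delivered content.

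The matter at stake is what the result may be said to show. If the protocol is right, a report that follows the hypothesis as written would present β₃ as the benefit over usual care alone, and would present a null result as no benefit over usual care alone. Neither statement would be tested by a randomized arm. The distinction has some practical bearing, because Protocol 1b looks ahead to use in routine programs: if the approach proves effective, "these activities can easily be added to standard weight control interventions to increase their effectiveness". That sentence names no comparator, so it shows why the wording matters but does not settle which description is correct.

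**Working it through.** The question is one of wording, so the check is a side-by-side reading followed by one identity.

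**1. The arms in each document**

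| | Wise arm | Control arm |
|---|---|---|
| SAP, Primary Hypothesis | usual care + wise activities | usual care alone |
| Protocol 2a, Interventions | usual care + wise activities | usual care + diet and physical activity videos and activities |

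The wise arm agrees; the control arm does not. Three protocol details fit its own version: the 9-delivery schedule is not split by arm, interest in receiving the online activities is an inclusion criterion for every family (section 4g), and control materials are explicitly described. Outside the SAP hypothesis, no text describes an arm given usual care only.

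**2. What β₃ estimates if the protocol is right**

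Let S(W), S(C) and S(U) be the mean BMI slopes under usual care plus wise activities, usual care plus control activities, and usual care alone.

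- β₃ = S(W) − S(C), the difference between the arms as randomized.
- Effect over usual care alone = S(W) − S(U) = β₃ + [S(C) − S(U)].

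The bracket is the effect of the control activities themselves. No arm would supply S(U), so the trial could not estimate it. The two quantities coincide only when the bracket is zero. The documents give neither its sign nor its size.

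**3. What β₃ estimates if the SAP is right**

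If no control content is delivered, S(C) = S(U), the bracket vanishes and the hypothesis is correct as written. The protocol's description of the control arm would then be the text to correct.

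**4. The plan's own figures**

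The power example is "a 0.6 BMI increase over 24 weeks in the control group and a 0.2 BMI increase over 24 weeks in the treatment group", and 0.6 − 0.2 = 0.4 kg/m², which agrees with the stated detectable difference per 24 weeks. The claim of at least 80% power with 80 children per arm comes from simulations whose standard deviations, ICCs and retention rates are not given, so it cannot be reproduced. It does not need to be for this point, since rewording the comparator changes no input to it.

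**The case against.** The best defense is that *alone* is one half of a pair: usual care alone against usual care plus the wise component. In that sentence it can fairly be read as meaning without the wise component. The protocol helps this reading, because it describes the control content as reinforcing what the program already teaches. The SAP's definition of β₃ as a between-arm difference is also correct whichever description holds. All of this stands, and it limits the consequence. It does not remove the mismatch: extra study-delivered content is not usual care alone, and a primary hypothesis should identify its comparator without help from another document.

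Three stronger readings are tempting, and the documents do not support them.

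- *β₃ is biased, or understates the benefit of the wise activities.* β₃ is valid for the arms as randomized. An understatement of the effect over usual care alone would require the control activities to lower BMI gain, and no text says so. The remark that both groups receive beneficial interventions may refer to the weight management program itself.
- *The control arm is a poor design choice.* Comparing wise content with other content delivered by the study is a legitimate test of the wise content. Only its name in the hypothesis is in question.
- *The power calculation assumed the wrong control group.* The 0.6 increase is offered only as an example among several simulated trajectories. In the linear model, power for β₃ depends on the 0.4 difference and not on the control group's absolute change.

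**Conclusion.** The inconsistency is real and neither document resolves it. It is minor. Conditional on the protocol's account being correct, the SAP hypothesis misnames the contrast that β₃ estimates, and the effect size and any null conclusion would need to be tied to usual care plus control activities.

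The gap between that contrast and the effect over usual care alone cannot be quantified from the documents. It may be small or zero, given how the control content is described. The model, the test, the stated power and the sample size are unchanged. It would go too far to say outright that the trial has the wrong comparator: that presupposes the protocol is right and the SAP wrong, which the documents leave open.

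**What to change.** Reconcile the SAP's Primary Hypothesis with Protocol 2a, Interventions. If the protocol describes the control arm correctly:

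1. Restate the primary hypothesis as usual care plus wise activities versus usual care plus diet and physical activity control activities.
2. Limit the reported effect size, and any null conclusion, to that contrast.

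If instead the SAP is correct, amend the protocol's description of the control arm.

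Under the first route the cost is a wording change in the SAP, with no change to analysis, sample size or conduct. The one downside is a narrower claim: the trial would speak to wise content against control content, both added to usual care, and not to benefit over usual care alone.

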Children and parents/guardians will complete data collection visits at 3 and 6 months post randomization. With the exception of demographic measures and a few baseline only measures, the 3- and 6-month visits will include measures previously collected at baseline. Fasting blood tests are included only at baseline and 6-month visits.

b. Procedure Risks

There are minimal risks in the research protocol. All research measures will be obtained by trained research assistants and phlebotomy by qualified phlebotomists at Quest Diagnostics, a nationwide commercial lab.

c. Use of Deception in the Study

There will be no deception used in the research.

d. Use of Audio and Video Recordings

No audio or video recording will occur by study staff.

As part of one of the intervention activities, children will be asked to upload a photo or a drawing to their individually assigned REDCap surveys. This image is similar to a profile image and designed to increase engagement. Children are instructed to not include photographs with faces.

Only qualified research staff will have access to images uploaded to REDCap.

e. Alternative Procedures or Courses of Treatment

No standard or alternative treatment will be withheld.

f. Will it be possible to continue the more (most) appropriate therapy for the participant(s) after the conclusion of the study?

No additional continuing treatment will be made available by the study after conclusion of the study.

g. Study Endpoint(s)

The main study endpoint is BMI change over 6 months, at the end of treatment. We do not plan to perform interim analyses of treatment

outcomes or terminate the study early for efficacy or futility because:

- Potential effects of the social psychological interventions are to
- mitigate drop out and increase perseverance with the treatment program over time.
- The interventions aim to affect weight gain trajectory and maintenance, intervention effects may not be observed over the short term.
- Alternatively, statistically significant short-term benefits may not reflect clinically significant health benefits over 6 months (the full length of the study).
- This study aims to calculate with some assurance the size of the difference between treatment outcomes (effect size) within reasonable confidence intervals, and to avoid bias in the estimates of effect sizes (because random high values in treatment effect may be used to justify early stopping, but rarely would random low values).

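### The primary model leaves the arms' baseline BMI means free to differ although baseline precedes randomisation: a small missed precision gain, recoverable with a common baseline mean if the within-child covariance is also enriched

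*SAP*

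**What the plan says.** The Protocol (section 2a) has height and weight measured at the second baseline call. It then states: "Families will be randomized to treatment conditions after completing baseline measures". Stratification is by location, sex and race/ethnicity, not by BMI. On follow-up: "Children and parents/guardians will complete data collection visits at 3 and 6 months post randomization".

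The SAP (Primary Analysis, Statistical Model and Approach) will "regress BMI at a given time point on study arm, days since randomization, and an interaction between study arm and days since randomization". Its equation carries β₁ for treatment, β₂ for time and β₃ for their product. The only other fixed effects are the stratification factors: "Finally, we include the randomization factors: sex and race/ethnicity". The child-level covariance is a random intercept: "γ_i is the subject-specific random intercept corresponding to the i^{th} child". A group-level random intercept is added. The target is plain: "We are interested in drawing inference around β_3 that represents the difference in BMI trajectory over time between the two study arms", and "we will use a two-sided Wald test at the 0.05 level of significance".

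No baseline-BMI covariate and no equal-baseline constraint appears. The SAP does not say outright that baseline BMI is one of the modelled outcomes. A 6-month trajectory with follow-up only at 3 and 6 months implies that it is.

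**The concern.** Randomisation makes the expected baseline BMI equal in the two arms, so any observed difference is chance. A free β₁ spends a parameter on that chance difference and gives up the information in baseline BMI about later BMI. If change is related to baseline level, a chance imbalance also moves β₃ in the sample at hand. The trial already collects the value needed to adjust for this. At stake are a slightly narrower interval for the primary effect and a rule, fixed in advance, for handling chance baseline imbalance, on which the SAP is silent.

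**Working it through.** **Inputs from the documents.** 80 children per arm, two-sided α of 0.05, at least 80% power for 0.4 kg/m² per 24 weeks (SAP, Detectable Difference, Sample Size, and Power). Visits at 0, 3 and 6 months, scaled to t = 0, 0.5, 1.

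**Assumed.** BMI SD 3 to 7 kg/m², no group clustering and, unless stated, complete data. The SAP's power simulations varied SD, ICCs and retention but no values are printed, so the 80% cannot be reproduced independently. It is used below as the only anchor.

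**1. What β₃ estimates with β₁ free.** With complete visits and a random intercept, each arm's slope is the ordinary least-squares slope. The deviations of t from its mean are −0.5, 0 and 0.5, and their squares sum to 0.5. The weights on the visit means are therefore (−1, 0, +1). The 6-month effect is the difference in mean change from baseline, and the 3-month visit has zero weight. Sex and race/ethnicity main effects do not alter this. With missing or irregular visits it is approximate.

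**2. Back-solving the power claim.** SD of 24-week change = 0.4 / [(1.960 + 0.842) × √(2/80)] = 0.4 / 0.443 = 0.903. Under a random intercept, SD of change = σ√(2(1−ρ)), so ρ = 1 − 0.903²/(2σ²).

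**3. Gain from a common baseline.** For two visits, the variance with β₁ free is (2/n)·2σ²(1−ρ). With a common baseline mean it is (2/n)·σ²(1−ρ²). The ratio is (1+ρ)/2. Exact generalised least squares for three visits agrees to three decimals here. Child-equivalents are 160 × (1 − ratio). The average shift of the current estimate for a one-SE baseline imbalance is (1−ρ)·σ·√(2/80).

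| BMI SD | ρ | Variance ratio | Power, from 80.0% | Child-equivalents | Shift, kg/m² |
|---|---|---|---|---|---|
| 3 | 0.955 | 0.977 | 80.9% | 3.7 | 0.021 |
| 4 | 0.975 | 0.987 | 80.5% | 2.0 | 0.016 |
| 5 | 0.984 | 0.992 | 80.3% | 1.3 | 0.013 |
| 6 | 0.989 | 0.994 | 80.2% | 0.9 | 0.011 |
| 7 | 0.992 | 0.996 | 80.2% | 0.7 | 0.009 |

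With 72 or 64 analysed per arm, the SD of change needed for 80% power falls to 0.857 or 0.808. The ratios then run from 0.980 to 0.996 and from 0.982 to 0.997, so the gain is slightly smaller.

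**4. Lower correlation.** The ratio is 0.949 at ρ = 0.90 and 0.897 at ρ = 0.80. But ρ = 0.90 with SD 5 gives an SD of change of 5 × √0.2 = 2.24, far above 0.903, so it does not fit the power claim.

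**5. Does the constraint ever lose?** Suppose children's slopes vary. Assume slope SD 0.5 or 0.8 kg/m² per 24 weeks, BMI SD 4 to 6, and SD of change held at 0.903. The table gives the true variance with β₁ dropped, relative to β₁ free.

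| Slope–baseline correlation | Random intercept only | Correct random-slope covariance |
|---|---|---|
| −0.4 | 0.950–0.969 | 0.857–0.926 |
| −0.2 | 0.973–0.984 | 0.960–0.974 |
| 0 | 0.994–1.001 | 0.994–0.9997 |
| +0.2 | 1.011–1.024 | 0.974–0.999 |
| +0.4 | 1.024–1.045 | 0.886–0.980 |

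Under the random intercept alone the constraint can cost about 1% to 4.5% of variance. With a covariance that lets slopes vary, it never lost in these runs.

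**6. Direction of the imbalance effect.** In the same set-up, the regression of 24-week BMI on baseline BMI is 0.955 to 0.976 at correlation −0.2, and 1.007 to 1.034 at +0.2. Below 1, the arm that starts heavier shows relatively less gain. Above 1, it shows more.

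**The case against.** Arm, time and arm-by-time is a standard specification. It matches the Protocol's endpoint of BMI change over 6 months (section 2g), and the gain at the design's own calibration is about one to four children out of 160. All of that stands, and it is why this is an optional improvement.

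Four stronger readings are tempting, and the documents do not support them.

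- A reader might infer that β₃ is biased. It is not: over randomisations it is unbiased with β₁ free.
- A reader might infer that the arm starting heavier by chance will always show the larger fall. That depends on how change correlates with baseline, which the documents do not give.
- A reader might infer that the SAP's statement that its model "has advantages over a t-test endpoint analysis and other repeated measures analysis approaches" is wrong. The advantages it lists are use of all available data, unequal follow-up, irregular intervals and missing data. The change-score identity, which holds for complete data, leaves them untouched.
- A reader might infer that deleting β₁ is free. Under the SAP's random-intercept covariance it can lose precision, by more than it gains at the larger assumed SDs.

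One point on the other side remains. Because the SAP prints no SD, ICC or retention, the documents do not bound the gain. It would be larger if the within-child correlation proved lower than the power claim implies.

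**Conclusion.** The point holds as a minor efficiency suggestion. As written, β₃ is a valid contrast that, with complete and equally spaced visits, equals an unadjusted change-score difference. A common baseline mean would adjust for a value already collected. If the power claim is right and BMI SD is 3 to 7 kg/m², the gain is about 0.4% to 2.3% of variance, or 0.2 to 0.9 power points. A one-SE baseline imbalance then moves the current estimate by about 0.01 to 0.02 kg/m² against a target of 0.4.

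These sizes rest on the assumed SDs, no group clustering and equal correlation between visits. The benefit is assured only when the constraint is paired with a covariance that lets children's slopes vary.

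**What to change.** Amend the SAP before unblinding:

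1. State that the pre-randomisation BMI is the time-0 outcome record.
2. Remove the treatment main effect so that both arms share one baseline mean, and keep the two-sided Wald test on β₃.
3. Replace the child-level random intercept alone with a random intercept and correlated random slope, or an unstructured within-child covariance over the three visits.
4. Apply the same constraint in the multiple-imputation sensitivity analysis (SAP, Intent-to-Treat).

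This needs no new data, visits or participants. One mean parameter is saved. The correlated slope adds two covariance parameters (slope variance and covariance). The unstructured form has six in place of two. The gain is negligible if change is nearly uncorrelated with baseline.

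The richer covariance may also widen the reported standard error. In the step 5 scenarios, the random-intercept model's standard error for β₃ is 8% to 22% too small with β₁ free, so that widening would be a correction. If the sponsor prefers to keep the random intercept alone, dropping β₁ should not be described as cost-free.
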